Background, Significance and Rationale

Background, Significance and Rationale

Previous research has suggested that the endocannabinoid system may serve a regulatory function in frontal-striatal brain circuits which have been implicated in anxiety disorders and Obsessive Compulsive Disorder (OCD) (Lutz et al. 2015, Gremel et al. 2016). In addition, there is an emerging body of evidence which demonstrates a potential role for drugs that target cannabinoid receptors in the treatment of anxiety disorders and Tourette's syndrome (Curtis et al. 2009, Müller-Vahl et al. 2013, Blessing et al. 2015). Data from animal studies (Deiana et al. 2011, Nardo et al. 2013, Breuer et al. 2016) suggest a potential benefit to these compounds in OCD as well. However, to date studies in humans are limited to case reports (Schindler et al. 2008). The purpose of this double-blind, placebo-controlled, within-subject study is to examine the effects of different cannabinoids, delivered in a laboratory setting, on adults with primary OCD. In order to accomplish this, adults with OCD who are also occasional marijuana smokers will be recruited for 3 outpatient laboratory sessions over the course of 2-3 weeks. In the laboratory, patients will receive different combinations of the cannabinoids tetrahydrocannabinol (THC, the active ingredient in the marijuana plant) and cannabidiol (CBD, a cannabinoid constituent of marijuana which has demonstrated therapeutic potential across a variety of psychiatric disorders including depression, anxiety, and psychosis [Campos et al. 2012]) or placebo. We will then measure whether or not patients respond to these agents (i.e. experience a significant reduction in their OCD symptoms) in the acute setting.

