Subjects may be receiving either psychotherapy or medication management in the community while they participate in this study; however, they will not be eligible for participation in this study if they a) are taking a selective SRI or clomipramine and have altered their dose in the 6 weeks prior to study enrollment or are planning to make changes to their medications during the period of the study (approximately 3 weeks), b) are taking psychotropic medications other than selective SRIs or clomipramine, or c) have begun cognitive-behavioral therapy within 8 weeks prior to enrollment or plan to commence cognitive-behavioral therapy during the period of the study (approximately 3 weeks). For subjects who are not currently receiving any treatment for OCD and are interested, referrals for external treatment providers will be given.”

Eligible subjects who have finished other studies in the Anxiety Disorders Clinic will be offered participation if they are eligible. These protocols will include:

IRB#6628 Attaining and maintaining wellness in OCD

IRB#7000 Control and Reward Circuits in OCD

IRB#7127 Toward Precision Medicine for OCD

IRB#7059 Pilot study of personalized-computerized inhibitory control training for OCD

IRB#6837 Internet Based Treatment for OCD (iCBT)

IRB#7239 Cannabinoid Medication for Adults with OCD

IRB#7572 Feasibility, Acceptability and Preliminary Efficacy of a Mobile App (nOCD) for OCD

Inclusion/Exclusion Criteria

Name the subject group/sub sample

Adults with OCD

Create or insert table to describe the inclusion criteria and methods to ascertain them

- 1. Patient must be 21-55 years of age at the time of consent
Clinical interview
- 2. Patient must be physically healthy male or non-pregnant female. Females of childbearing potential must comply with contraceptive restrictions noted in the protocol.
Clinical interview by trained M.D. or Ph.D., physical examination by M.D., ECG, and blood tests
- 3. Patients must fulfill DSM 5 criteria for OCD, OCD being the principal disorder (i.e., currently the most severe and needing of treatment), and have had OCD for at least one year with near-constant symptoms.
Clinical Interview by trained M.D. or Ph.D. and results of SCID
- 4. Patients with a Y-BOCS score of greater than or equal to 16 prior to entering trial.
Clinical interview and assessment by trained rater
- 5. Patient has smoked marijuana at least once in the past and did not experience intolerable side effects.
Clinical Interview

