protocol with the volunteer and document their consent to the research study. The physician and volunteer will then sign the study consent form.

4) Study procedures will begin after the study physician verifies that the participant meets inclusion/exclusion criteria, understands the medical risks of participation, and is capable of providing informed consent. [name], the senior study physician, will settle any disagreements among the study team as to a volunteer's eligibility, and will make the final decision as to study participation. Behavioral observations and testing will be carried out by one of the study clinicians. In the event of an emergency, one of the study physicians will be available by phone. [name] and other psychologists, nurses, and physicians are around the corner or down a corridor from the outpatient laboratory. We do not test research participants unless we are sure that a physician is available by telephone or by pager in the event of an emergency. A set of emergency procedures, including a list of physicians, telephone and pager numbers is posted in the outpatient laboratory.

Medication: Patients will be administered smoked marijuana at one of the following concentrations: High THC (5-10%)/Low CBD (<1%), Low THC (<1%)/High CBD (>10%), or placebo (0% THC and CBD). The order in which they receive each concentration will be randomized. Participants will complete 1 or 2 sessions per week depending on timing and subject availability. Because of cannabidiol's long terminal half-life (21-33 hours), we are allowing time for drug clearance in between sessions (at least 3 days) to avoid potential carryover effects (Consroe et al., 1991).

General Design: There will be three 4-hour laboratory sessions, which will occur between 0900 and 1300 hr, testing the effect of smoked marijuana on OCD symptoms. Sessions will occur once or twice per week over a period of approximately 3 weeks depending on each participant's availability.

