Laboratory Sessions: Participants will be instructed that they should not smoke either marijuana or cigarettes on the morning of a session (beginning at midnight). We will do a carbon monoxide (CO) test upon their arrival in the laboratory to verify nothing was recently smoked. Participants will also be given a breathalyzer test to ensure that they did not drink alcohol prior to arrival. At each visit, urine samples will be tested for drug use, and, for women of child-bearing age, for pregnancy. Subjects who are found to be pregnant will be discontinued from the study, but will receive payment for those procedures that they have already completed. Participants with high COs or those testing positive for drugs other than marijuana will be re-scheduled and possibly excluded from further participation. Patients will then receive either high THC (5-10%)/low CBD (<1%) marijuana, low THC (<1%)/high CBD (>10%) marijuana, or placebo (0% THC and CBD). The marijuana used in the study will be provided by the NIDA. We will guide participants through smoking individual puffs of marijuana using cue-dosing procedures until 50% of the cigarette has been smoked. Specifically, for each puff, participants will be instructed to inhale for 5 seconds and hold each puff in the lungs for 10 seconds. There will be approximately a 40-second interval between each puff. For the first hour after marijuana administration, clinical ratings, scales, and BP/HR will be obtained every 20 minutes. During the second hour, these measures will be repeated once every half-hour, and then again at the conclusion of the third hour (see Table 1). The session will end after the third hour. Participants will be allowed to leave the facility when they pass the field sobriety test, and will be instructed not to drive a car or use other drugs or alcohol for at least 8 hours after marijuana administration.

Table 1. Session Schedule

| TIME (min) | EVENT |
|------------|--|
| -50 | CO, collect urine, breathalyzer, start breakfast |
| -30 | Finish breakfast (set timer for 30 min), balance, TLFB, BP/HR, VAS, YBOCCS, STAI |
| 0 | Marijuana administration |
| 20 | BP/HR, VAS, YBOCCS, MRF, STAI |
| 40 | BP/HR, VAS, YBOCCS, MRF, STAI |
| 60 | BP/HR, VAS, YBOCCS, MRF, STAI |
| 90 | BP/HR, VAS, YBOCCS, MRF, STAI |
| 120 | BP/HR, VAS, YBOCCS, MRF, STAI |
| 180 | BP/HR, VAS, YBOCCS, MRF, STAI, Field Sobriety Test, participant discharge |

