There are also possible side effects following CBD administration. The medication has few psychoactive effects (e.g., Leweke et al., 2000; Fusar-Poli et al., 2009), although there is a report of decreased anxiety and increased sedation (400 mg; Crippa et al., 2004). One placebo-controlled study administered CBD (approximately 700 mg/day) to patients with Huntington's disease for 6 weeks and reported no significant adverse effect from the medication relative to placebo (Consroe et al., 1991). CBD doses up to 1500 mg/day have been given for several weeks to schizophrenic patients with no side effects reported (Zuardi et al., 1995, 2006).

Describe procedures for minimizing risks

All participants are fully informed of these effects, and because all currently smoke marijuana, these effects should be familiar to them.

The risks of marijuana and/or CBD exposure to a developing fetus or newborn are unknown, so women who participate in the study will be required to confirm that they are not pregnant or breastfeeding and are practicing an effective form of contraception (e.g. hormonal contraception or barrier methods) throughout the duration of the study.

In previous studies, participants have not found the study procedures to be stressful or difficult. They are monitored continuously throughout the experimental procedure. Emergency medical equipment is available in our laboratory, which is located in a hospital where a full medical emergency back-up team is constantly available. We anticipate that careful participant selection, dose selection and monitoring will obviate the need for such emergency care.

Methods to Protect Confidentiality

Describe methods to protect confidentiality

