Patients will be required to take public transportation to and from the laboratory each session, for which they will be reimbursed. We will pay for mass-transit expenses in cash during each visit in a total of \$6.00 per visit (to cover \$2.75 subway fare to and from the laboratory). At the end of each laboratory session, study clinicians will conduct the Field Sobriety Test. After confirming that the participant has passed the Field Sobriety Test, the patient will be allowed to leave the laboratory. If a participant is still impaired at the end of the session, she or he will be asked to remain in the laboratory until the effects wear off, and will be paid extra (i.e. \$10 per hour for any additional time in the laboratory).

For participating in this study subjects will receive cash for each laboratory session they complete. They will earn \$25 for each session, and an additional bonus of \$50 if they complete the study. If they withdraw early they will not receive the bonus payment. Session pay will be given in cash at the end **each session.** of

~~the third session if all the sessions are completed. If subjects withdraw from the study, they will be given cash for the sessions completed at that time.~~ In total, the pay for study participation will be \$125 for completion of all sessions.

References

References

4. Müller-Vahl KR. Treatment of Tourette syndrome with cannabinoids (2013) *Behav Neurol.* 27(1): 119-124.

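### Contraception is required only for the duration of the study, with no stated period after the last dose, so the rule can lapse before study CBD has cleared (minor)

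*Combined protocol and SAP*

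**What the plan says.** All references are to the combined protocol and SAP.

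- **The rule.** The section on procedures for minimizing risks gives unknown fetal and newborn risk from marijuana or CBD as the reason for contraception. Women must confirm that they are not pregnant or breastfeeding and that they "are practicing an effective form of contraception (e.g. hormonal contraception or barrier methods) throughout the duration of the study".
- **Eligibility.** Inclusion criterion 2 refers back to the protocol's contraceptive restrictions. Criterion 9 asks for effective birth control. Neither states a duration.
- **Clearance.** Under Study Procedures (Medication), the protocol describes CBD's "long terminal half-life (21-33 hours), we are allowing time for drug clearance in between sessions (at least 3 days"). The order of the three conditions is randomized.
- **Length of the study.** The Background says participants "will be recruited for 3 outpatient laboratory sessions over the course of 2-3 weeks". General Design says "Sessions will occur once or twice per week over a period of approximately 3 weeks". Concurrent Research Studies excludes people "planning to make changes to their medications during the period of the study (approximately 3 weeks").
- **End of participation.** Table 1 ends with discharge at 180 minutes. Under Compensation, a bonus is paid "if they complete the study. If they withdraw early they will not receive the bonus payment", and the total is stated "for completion of all sessions".
- **Instructions after dosing.** Participants "will be instructed not to drive a car or use other drugs or alcohol for at least 8 hours after marijuana administration". Contraception is not part of this instruction. Pregnancy tests are done before each session; none is described after the last dose.

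**The concern.** The purpose of the rule is tied to exposure, but its end is tied to the study calendar. If the study ends for a participant at her third session, or when she withdraws, the requirement stops while the last dose may still be present. The protocol treats residual CBD as important enough to space the sessions by at least 3 days to avoid carryover, yet sets no matching period after the final dose for a fetal risk it calls unknown. At stake is whether a safety rule covers the exposure it was written for. Efficacy estimates are not involved.

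**Working it through.** The plan has no figure of its own to reproduce here. The check has two parts: when the requirement ends, and what remains of a CBD dose after that.

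**1. When the requirement ends**

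The duration of the study is not defined, so the passages have to be set side by side.

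- Session pay is $25 for each of three sessions and the bonus for completing the study is $50. 3 × 25 + 50 = 125, which is the total given for completing all sessions. Completing the sessions therefore counts as completing the study.
- The last scheduled event is discharge 3 hours after dosing in session 3. No later visit is described.
- The study period of roughly 3 weeks in Concurrent Research Studies might be read as a fixed span that outlasts session 3. For a woman with two sessions a week it could. But General Design gives the same span to the sessions themselves, so a period of cover after the last dose is not secured.
- For a woman who withdraws after a dose, no continuing requirement is stated.

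**2. What remains of a CBD dose**

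Input: half-life 21-33 hours (Study Procedures, Medication). Formula, assuming simple terminal-phase decay: fraction remaining = 0.5^(t / half-life), with t in hours since the dose.

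| Time since CBD dose | Half-life 21 h | Half-life 33 h |
|---|---|---|
| 3 h (discharge) | 0.5^(3/21) = 90.6% | 0.5^(3/33) = 93.9% |
| 72 h (3 days) | 0.5^(72/21) = 9.3% | 0.5^(72/33) = 22.0% |
| 168 h (7 days) | 0.5^(168/21) = 0.4% | 0.5^(168/33) = 2.9% |

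If CBD is given in session 2 and session 3 follows at the minimum 72 hours, discharge from session 3 comes 75 hours after the CBD dose, with 8.4% to 20.7% remaining.

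The early figures are probably too high. Applying the terminal half-life from time zero ignores the faster distribution phase after a single smoked dose. The half-life is also cited to a study that the protocol describes elsewhere as giving about 700 mg a day for 6 weeks, whereas here half of one cigarette is smoked. The protocol itself nevertheless applies this half-life to these sessions.

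**3. How many women could have CBD last**

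Assuming balanced orders, and using the protocol's expected 1:1 sex ratio: 15 completers × 1/2 × 1/3 = 2.5 women, or fewer if some are not of childbearing potential. This counts women whose last dose is CBD. It does not estimate harm.

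No THC half-life is given, so nothing is computed for women whose last dose is high THC.

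**The case against.** The strongest reply is that the gap makes almost no practical difference. Women must already be using effective contraception at entry, and nothing in the design prompts them to stop. The risk section says every participant is a current marijuana smoker. Their own marijuana use is restricted only from midnight before a session; inclusion 6 is an 8-week look-back at entry and sets no limit during or after the study. Against that background, the tail of half a study cigarette adds little avoidable exposure. This stands, and it is why the point is minor. It does not remove the point, because the protocol imposes contraception on this same population, and its rule still stops too early for its stated reason.

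A second reply is that the consent form may already state a longer period. It is listed among the uploads but is not visible here, so only the protocol text can be called silent. That also stands, and the consent-form part of the fix is conditional on it.

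A third reply is that the documents set no residual level relevant to pregnancy. The 3-day interval was chosen against carryover, and any clearance threshold comes from outside. This is correct. The point therefore rests on the absence of any stated period after the last dose, with the decay figures showing only the order of magnitude.

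A reader might go further and infer that the trial exposes women to a material fetal risk. The documents do not support that. Harm would require a woman to stop contraception within days of a last dose and conceive, and nothing in the documents suggests this is likely.

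**Conclusion.** The point holds as a minor safety-wording gap. The visible protocol requires contraception only while the study lasts, and the pay rules and session schedule place study completion at session 3. On the protocol's own half-life, about 9-22% of a last CBD dose would remain at 3 days and 0.4-2.9% at 7 days. The requirement can therefore lapse before the exposure has cleared, both for completers with CBD last and for women who withdraw after a CBD dose. Early withdrawal is expected (20 enrolled for 15 completers) and has occurred (two of the first five participants), although whether those two had been dosed is not stated.

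The size rests on simple terminal-phase decay and on carrying the cited half-life over to half a smoked cigarette; the early percentages are best read as upper-end values. The added risk is very small. It should not be inferred that participants receive no instruction on contraception after dosing, since the consent form has not been seen. Endpoints, analysis and trial conclusions are unaffected.

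**What to change.** Amend the contraception sentence in the section on minimizing risks so that contraception continues for a fixed period after the last dose received, about 7 days, including after early withdrawal. Make the same change in the consent form if it does not already say so. Inclusion 2 already points to the protocol's restrictions, so it would pick up the new wording.

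Apply one rule to all women regardless of order, which also protects the blind. The 7 days come from the CBD half-life alone, so the study physician should confirm the length with THC considered. The reminder can be given at discharge with the existing 8-hour instruction.

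The cost is one sentence in the protocol, possibly one in the consent form, and about one extra week of contraception for women who already use it. No extra visit or test is needed. Enrollment was still open at the time of the continuation report, so the change could still apply to later participants.

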Cannabis Effects: We will use a random-effects linear mixed model to evaluate changes in each continuous outcome (YBOCCS, OCD-VAS, STAI-S MRF, cardiovascular measures) as a function of condition (THC, CBD, placebo), time point, and their interaction. Mixed-effects modeling accounts for clustering of repeated measures within subjects, allows time to be modeled as a continuous rather than categorically, and has been used in similar acute pharmacological challenge studies (Rodriguez et al. 2013). The model will include participants as a random effect, condition and time as fixed within-subjects factors, the interaction between condition and time, and a random intercept. Given that the interval between sessions increases over the course of each session, we will model time as a continuous variable. We will use contrasts within each mixed-effects linear regression model to estimate differences in outcomes between both active cannabis varieties and placebo at different time points. All statistical tests will be conducted using an alpha level of 0.05, two-tailed.

Other Effects: Though we have no a priori hypotheses about the effects of age, gender, comorbid diagnoses (e.g. MDD), or other factors that might influence our participants' response to cannabis, we will nonetheless explore the possibility of such effects by including these factors as covariates in separate analyses.

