** BP/HR = blood pressure and heart rate; VAS = Visual Analogue Scale; YBOCCS = Yale-Brown Obsessive-Compulsive Challenge Scale; MRF = Marijuana Rating Form; STAI = State/Trait Anxiety Inventory; TLFB = Marijuana Timeline Followback

Patients will be required to take public transportation to and from the laboratory each session, for which they will be reimbursed. Study clinicians will conduct the Field Sobriety Test. After confirming that the participant has passed the Field Sobriety Test, the patient will be allowed to leave the laboratory. If a participant is still impaired at the end of the session, she or he will be asked to remain in the laboratory until the effects wear off, and will be paid extra (i.e. \$10 per hour for any additional time in the laboratory). In the event that the impairment does not resolve in a timely manner, a study physician will determine whether the person can leave the laboratory or if further action is needed. It is worth noting that in our experience, it is exceedingly rare (<1% of all participants) for marijuana smokers to remain intoxicated several hours after smoking marijuana in the laboratory.

Laboratory Facility: Experimental sessions will be conducted in the Substance Use Research Center (SURC) located on the 3rd floor of the NYS Psychiatric Institute.

Safety Measures: Vital signs (heart rate and blood pressure) will be monitored in each session. If SBP > 180 mmHg, DP > 110 mmHg, or HR > 120 bpm, these measures will be taken 2 additional times at 2 min intervals: A physician will see the participant immediately if blood pressure or heart rate remain above these levels for 3 continuous readings.

Data Analysis: A between and within-subject repeated measures analysis of variance (ANOVA) with planned comparisons will be implemented to determine the effects of marijuana on OCD symptoms

You can upload charts or diagrams if any

Criteria for Early Discontinuation

Criteria for Early Discontinuation

Participants are free to withdraw from the study at any time for any reason. Study doctors are to discontinue patients from the study if patients:

- Request an early discontinuation or withdraw consent.
- Experience a serious or intolerable adverse event that prevents the patient from continuing.

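### The mixed model has a participant intercept but no session term or within-session correlation, so active-versus-placebo contrasts get standard errors that are too small whenever ratings within a session are correlated

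*Combined protocol and SAP*

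**What the plan says.** The Cannabis Effects part of the Data Analytic Plan sets out one model for every continuous outcome: "The model will include participants as a random effect, condition and time as fixed within-subjects factors", plus the condition-by-time interaction and a random intercept. The only clustering it mentions is within subjects. Its contrasts are meant to "estimate differences in outcomes between both active cannabis varieties and placebo at different time points", and "All statistical tests will be conducted using an alpha level of 0.05, two-tailed". It specifies no session or participant-by-condition term, no residual covariance, no robust standard error and no degrees-of-freedom method. Its one use of the word session concerns the spacing of time: "Given that the interval between sessions increases over the course of each session, we will model time as a continuous variable".

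Under Study Procedures, General Design states "There will be three 4-hour laboratory sessions", and the Medication paragraph gives one condition per session, in random order, at least 3 days apart. Table 1 has one pre-dose set of ratings at -30 minutes ("Finish breakfast (set timer for 30 min), balance, TLFB, BP/HR, VAS, YBOCCS, STAI"), which does not include the Marijuana Rating Form (MRF). After dosing, "For the first hour after marijuana administration, clinical ratings, scales, and BP/HR will be obtained every 20 minutes", and then at 90, 120 and 180 minutes. That makes 7 ratings per session, or 6 for the MRF.

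The Data Analysis paragraph under Study Procedures describes a different method for the same question: "A between and within-subject repeated measures analysis of variance (ANOVA) with planned comparisons will be implemented". It gives no error term, and neither description is said to govern.

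**The concern.** Within a participant, session and condition are the same thing. Anything that makes one day differ from another (sleep, stress, recent symptoms, rater) enters the active-minus-placebo difference in full and does not average out over the ratings of that day. A participant intercept removes only what is common to all three days. Without a session term, the model treats the day's shared deviation as rating noise and divides it by the number of ratings.

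The sole hypothesis, that both active varieties reduce symptoms relative to placebo, rests on these contrasts. If their standard errors are too small, ordinary day-to-day variation can be reported as an acute cannabis effect. The plan also speaks of evaluating changes in each outcome without saying whether the session baseline is a response time point, a covariate or is subtracted. Subtraction is not a cure: every change score in a session then carries the same baseline error.

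**Working it through.** **Benchmark.** The documents give 15 completers but no effect size, SD or power, so the sample size cannot be reproduced. The figure to test is the stated two-sided alpha of 0.05.

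**Inputs from the documents.** n = 15; 3 sessions, one per condition; ratings at -30, 20, 40, 60, 90, 120 and 180 minutes (m = 7); time continuous, taken here as linear.

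**Assumption.** Within-person variance is set to 1 and split into rho (session) and 1 − rho (rating). The documents give neither part; rho is taken from 0 to 0.5.

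**Formulas.** Mean time is 480/7 = 68.6 min. Sxx = 61,400 − 480²/7 = 28,486. For a contrast at time t, h = 1/7 + (t − 68.6)²/Sxx, so h = 0.145 at 60 min and 0.579 at 180 min.

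- True variance: (2/15) × [rho + (1 − rho)h].
- Variance reported by the planned model: (2/15) × h × [(1 − rho) + rho × 196/295].

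The residual df are 315 ratings − 15 participants − 5 fixed effects = 295. The factor 196 is 28 × 7: session deviations have (15 − 1)(3 − 1) = 28 df, each spread over 7 ratings.

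**Direction.** Since h never exceeds 0.58 and 196/295 = 0.664, h × 0.664 × rho is below rho at every scheduled time. The reported variance is therefore too small for any rho above 0.

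**Worked case, 60 min, rho = 0.3.** True: 0.3 + 0.7 × 0.1454 = 0.4018. Reported: 0.1454 × (0.7 + 0.3 × 0.664) = 0.1308. The SE ratio is √(0.4018/0.1308) = 1.75. A critical value of 1.97 then acts like 1.97/1.75 = 1.12, whose two-sided normal tail is about 26%.

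**Null simulation of the planned model** (20,000 trials per setting, raw ratings as response):

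| rho | true SE / model SE, 60 min | true SE / model SE, 180 min | type I, 20 min | type I, 60 min | type I, 120 min | type I, 180 min |
|---|---|---|---|---|---|---|
| 0 | 1.00 | 1.00 | 5% | 5% | 5% | 5% |
| 0.1 | 1.28 | 1.05 | 10% | 12–13% | 9–10% | 6% |
| 0.3 | 1.75 | 1.16 | 19% | 26% | 19% | 9% |
| 0.5 | 2.18 | 1.28 | 28% | 37% | 27% | 13% |

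**Other readings of the plan.**

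- *Change from session baseline* (6 scores, 250 df): about 30% at 60 min and 11% at 180 min for every rho from 0 to 0.5. The shared baseline error has the same variance as the rating error, so it acts like a session share of one half.
- *Session baseline as covariate* (3,000 trials): 10%, 17% and 22% at 60 min, and 6%, 7% and 9% at 180 min, at rho 0.1, 0.3 and 0.5.
- *MRF, 6 raw ratings:* 10%, 20% and 30% at 60 min at the same rho values.
- *Serial correlation of 0.8 per 20 min:* 34–36% at 60 min and 16–17% at 180 min.
- *Session slopes with SD 0.3 per hour, rho 0.2:* 21% at 60 min and 19% at 180 min.

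**Condition-by-time slope test.** A pure level shift cancels from the slope but inflates the residual, so the test is conservative: 4%, 3% and 1% at rho 0.1, 0.3 and 0.5. With the session slopes above it rejects 9%, and with the serial correlation above 11%.

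**Check of the remedy.** A REML fit with participant intercept plus session intercept and slope, with Satterthwaite df, gave 3.0–5.0% at 20, 60, 120 and 180 min and 2.9–4.6% for the slope. This covered six settings with 3,000 fits each. Fitting one line per session and analysing its value by participant and condition on 28 df gave 4.6–5.4%.

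**The case against.** **The plan is brief, and silence is not exclusion.** Naming both participants as a random effect and a random intercept is loose, and an analyst might add a session term. But the paragraph lists its terms, and the only clustering it names is within subjects. If a session term is intended, it should be written down before unblinding.

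**The size is assumed.** This stands: no variance is given, and at rho 0 with raw, serially independent ratings there is no error. The direction does not depend on the size, though, and a rho of only 0.1 already more than doubles the error at 60 minutes.

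**60 minutes is near the worst case.** True: it lies close to the mean rating time, and no primary time point is named. At 180 minutes the range for raw ratings is only 5–13%. Baseline as a covariate is milder too, but still inflated.

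**The ANOVA might be sound.** With a participant-by-condition error term it would avoid this fault for the condition effect. No error term is stated, and the Data Analytic Plan describes the mixed model.

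**A session slope is a lot for 15 people.** A session intercept alone controls the error under a pure level shift: 4.0% and 3.5% at 60 minutes at rho 0.3 and 0.5, in 200 fits each. The slope term is needed if sessions differ in trend. A singular fit is a real possibility, so a fallback is needed.

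**Conclusion.** The concern holds and should be fixed before the data are unblinded. Fitted as written, the model tests active-versus-placebo differences at time points with standard errors that are too small whenever ratings within a session are more alike than ratings from the same person's other sessions. For raw ratings, actual type I error runs from 5% to 37% at 60 minutes and from 5% to 13% at 180 minutes over rho 0 to 0.5. For change scores it is about 30% and 11% at those times, whatever rho is.

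These sizes rest on an assumed rho, linear time and complete data from 15 participants. The conclusion is confined to contrasts at time points; the condition-by-time slope test can err in either direction.

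**What to change.** In the Data Analytic Plan, Cannabis Effects:

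1. Add a random intercept and a random time slope for session nested within participant. Alternatively, specify a within-session residual covariance suited to unequal spacing. Fix the choice before unblinding.
2. Use Kenward-Roger or Satterthwaite degrees of freedom (about 28 for session-average contrasts, somewhat more at late time points).
3. State whether the session baseline is a response time point or a covariate, with a separate rule for the MRF, which has no baseline.
4. Pre-specify a fallback for a singular fit: fit a line per session, take its value at each time point, and analyse it by participant and condition on 28 degrees of freedom.
5. As an editorial matter, the sentence on time spacing should refer to the interval between ratings.

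In the Data Analysis paragraph under Study Procedures, replace the ANOVA sentence with a reference to this model.

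The cost is SAP wording and one or two lines of code. Reported intervals will be wider, the model may fit singularly with 15 people, and the test is mildly conservative (about 3%) if there is truly no session variance. The application reports enrollment ongoing, with 2 of 5 enrolled participants having completed, and the change needs no new data.
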